In order to determine an appropriate sample size, an a priori power analysis was performed. We chose to use isometric quadriceps strength at two weeks as the primary outcome variable. Using an alpha level of 0.05 and the standard deviation and minimal clinically important difference reported by Husted et al. (Trials, 2018) of 0.22 Nm/kg and 0.15 Nm/kg, respectively, a sample size of 70 total patients (35 patients per group) would be 80% powered to detect clinically important differences (G*Power, version 3.1).

Data collection will coincide with four regularly-scheduled patient visits: preoperative and 2, 6, and 12 weeks after surgery. Participants will complete isometric quadriceps testing at each study visit, and will be asked to complete the KOOS,JR, VR-12, and VAS pain scale questionnaires. We will also record the participant's opioid consumption per our standard of care, as well as whether the patient is able to walk without an assistive device and/or self-reports the ability to navigate stairs. Beginning at the 6-week postoperative visit, patients will be asked to complete the five times sit-to-stand test. The primary outcome variable, isometric quadriceps strength at 2 weeks, will be compared between groups using a two-tailed independent t-test. All continuous secondary variables will be assessed using group x time repeated measures ANOVAs. The prevalence of patients that can walk without an assistive device and/or navigate stairs at 2, 6, and 12 weeks will be compared between groups using chi-square or Fisher Exact tests as appropriate.

Attachments

Subject Recruitment Methods & Advertising

Describe how the study team will identify and recruit subjects. Please consider the following items and provide additional information as needed so that the IRB can follow each step of the recruitment process.

- How will the study team identify potential participants?
- Who will first contact the potential subjects, and how?
- Will you use advertisements? If so, how will you distribute those?
- How and where will the research team meet with potential participants?
- If applicable, describe proposed outreach programs for recruiting women, minorities, or disparate populations.
- How you will minimize undue influence in recruitment?
- Attach copies of all recruiting and advertising materials (emails, verbal scripts, flyers, posts, messages, etc.).

For additional information on recruiting and advertising:

- [IRB Application Instructions - Advertisements](#)

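### Sit-to-stand, measured only at 6 and 12 weeks, is analysed without a covariate although preoperative quadriceps strength is scheduled; adjusting for it would add precision at almost no cost

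*Combined protocol and SAP*

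**What the plan says.** All the relevant text on timing and analysis is in the Study Design section.

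- Visits: "Data collection will coincide with four regularly-scheduled patient visits: preoperative and 2, 6, and 12 weeks after surgery".
- Strength: "Participants will complete isometric quadriceps testing at each study visit". A preoperative value is therefore scheduled.
- Sit-to-stand: "Beginning at the 6-week postoperative visit, patients will be asked to complete the five times sit-to-stand test". That leaves two measurements, at 6 and 12 weeks.
- Secondary analysis: "All continuous secondary variables will be assessed using group x time repeated measures ANOVAs". No covariate is named, and the plan does not say whether the group term or the interaction is the test of interest.

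Research Procedures describes how the chair test is run but adds no preoperative assessment. It also omits the test at any visit where the participant cannot do one practice repetition without the armrests. The strength test described there includes a rest between legs, so both legs appear to be tested. Potential Risks & Benefits allows functional testing to be left out of a session if it is judged unsafe. A study flow chart is listed as an attachment but is not in the supplied text, so this reading rests on the written sections.

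**The concern.** Patient function is a stated objective, and sit-to-stand is the only timed functional task; walking aids and stairs come from a questionnaire. The other repeated outcomes scheduled from the preoperative visit (KOOS JR, VR-12, VAS) have their own preoperative value, so a group-by-time analysis can reflect change from before surgery. Sit-to-stand has none, and the plan puts nothing in its place.

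Two things follow.

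- **Precision.** With about 35 patients per arm, some chance difference in preoperative function is likely. The planned model neither adjusts for it nor uses a scheduled measurement that could explain part of the between-patient variation.
- **Interpretation.** With only two postoperative visits, the interaction asks solely whether the arms diverge or converge between week 6 and week 12. That is probably not the question a reader will want answered.

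**Working it through.** **1. The plan's own figure.** Study Design gives SD 0.22 Nm/kg, difference 0.15 Nm/kg, two-sided alpha 0.05 and 80% power for 2-week strength. The standardised difference is 0.15/0.22 = 0.682. The noncentral t calculation gives 34.75, rounded up to 35 per arm, or 70 in total, with power 80.3%. The stated sample size reproduces and is not in dispute.

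**2. Single-visit sensitivity for sit-to-stand, unadjusted.** The documents give no SD or target effect for this outcome, so work in SD units. With 35 evaluable per arm, 80% power and two-sided 0.05, the detectable difference is 0.679 SD. Power at 0.5 SD is 54%.

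**3. Effect of one covariate.** Let r be the correlation between preoperative strength and sit-to-stand time at a visit; its sign does not matter. The documents do not give r, so a range is assumed. Residual variance is 1 − r², the detectable difference is 0.679 × √(1 − r²), and the equivalent total sample is 70/(1 − r²). One degree of freedom is lost (2n − 3 = 67).

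| Assumed r | Variance removed | Equivalent total | Detectable difference | Power at 0.5 SD |
|---|---|---|---|---|
| 0 | 0% | 70 | 0.68 SD | 54% |
| 0.2 | 4% | 72.9 | 0.67 SD | 56% |
| 0.3 | 9% | 76.9 | 0.65 SD | 58% |
| 0.4 | 16% | 83.3 | 0.62 SD | 61% |
| 0.5 | 25% | 93.3 | 0.59 SD | 66% |

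**4. The planned two-visit group main effect.** This term averages the two visits. With between-visit correlation ρ (also not in the documents), the variance of the average is (1 + ρ)/2, and after adjustment it is (1 + ρ)/2 − r².

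- ρ = 0.5: unadjusted 0.679 × √0.75 = 0.59 SD. Adjusted: 0.679 × √0.71 = 0.57 SD at r = 0.2, and 0.679 × √0.50 = 0.48 SD at r = 0.5.
- ρ = 0.7: unadjusted 0.679 × √0.85 = 0.63 SD. Adjusted: 0.679 × √0.81 = 0.61 SD at r = 0.2, and 0.679 × √0.60 = 0.53 SD at r = 0.5.

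**5. Chance imbalance.** The standard error of a standardised baseline difference is √(2/35) = 0.239 SD. The probability that it exceeds 0.25 SD in either direction is about 30%. An imbalance of one standard error moves the sit-to-stand difference by r × 0.239: 0.05 SD at r = 0.2 and 0.12 SD at r = 0.5.

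**6. The interaction term.** If the true group difference is δ at both visits, the interaction is δ − δ = 0. The interaction test then rejects only at its alpha rate, however large δ is. The benefit appears in the group main effect alone.

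**The case against.** The strongest reply is that nothing here is an error. Patients are randomised, so comparing postoperative values between arms is valid without a baseline, and the test's standard error already allows for chance imbalance. The planned ANOVA supplies a valid group main effect. The outcome is secondary, and the gain rests on a correlation that the documents do not report. That correlation links an isometric strength measure to a timed whole-body task 6 to 12 weeks after joint replacement and could be low. At r = 0.2 the gain is nearly invisible. The primary comparison, which "will be compared between groups using a two-tailed independent t-test", also has no baseline adjustment, so it may seem odd to single out sit-to-stand.

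Most of this stands, and it sets the weight of the point. It does not remove the point: the covariate is already scheduled, the change is one sentence, and the choice of term in the ANOVA needs settling in any case.

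Several stronger readings are tempting, and the documents do not support them:

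- A reader might infer that the missing baseline biases the comparison. Randomisation rules that out.
- A reader might infer that preoperative imbalance passes in full into the result. It passes only in proportion to r (step 5).
- A reader might take 0.68 SD as the sensitivity of the planned analysis. It belongs to a single-visit comparison; the two-visit main effect starts lower (step 4).
- A reader might assume that every patient will have a preoperative strength value. It is scheduled for all, but unsafe testing may be skipped.

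**Conclusion.** The point holds as a minor, low-cost improvement to one secondary outcome. The planned sit-to-stand analysis is valid but leaves a scheduled preoperative measurement unused, and it does not say which ANOVA term answers the treatment question. The interaction cannot detect a benefit that is in place by 6 weeks and maintained.

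For an assumed r of 0.2 to 0.5, adjustment removes about 4% to 25% of single-visit variance and lowers the single-visit detectable difference from 0.68 SD to between 0.67 and 0.59 SD. For the two-visit main effect, the unadjusted value is about 0.59 to 0.63 SD if ρ is 0.5 to 0.7. All these figures assume 35 evaluable patients per arm, which is optimistic because patients who need the armrests are not tested at that visit. The primary analysis and the sample size of 70 are unaffected. A reader might also conclude that a preoperative chair test is required; it is not, because the scheduled strength test can serve as the covariate.

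**What to change.** Before allocation is revealed to the biostatistician, who is blinded under the plan, replace the general ANOVA sentence for this outcome with a specific one. Sit-to-stand time at 6 and 12 weeks is analysed in a repeated-measures model with group, visit, group by visit, and preoperative quadriceps strength of the operated leg as the single covariate. The adjusted group difference, with its confidence interval, is reported at each visit. State what is done for any participant whose preoperative strength test was skipped. If the sponsor prefers no adjustment, the plan should say so with a reason, and should name the group term or the visit-specific differences as the result of interest.

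The cost is a change of analysis wording and one degree of freedom for the covariate. It needs no new procedure, visit or patients.

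### The primary t-test at 2 weeks ignores preoperative quadriceps strength, which the trial already measures; adjusting for it would add precision at almost no cost.

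*Combined protocol and SAP*

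**What the plan says.** All the relevant text is in the Study Design section of the combined protocol and SAP.

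- Primary outcome: "We chose to use isometric quadriceps strength at two weeks as the primary outcome variable".
- Primary test: "The primary outcome variable, isometric quadriceps strength at 2 weeks, will be compared between groups using a two-tailed independent t-test". No covariate is named.
- Visits: "Data collection will coincide with four regularly-scheduled patient visits: preoperative and 2, 6, and 12 weeks after surgery".
- Strength testing: "Participants will complete isometric quadriceps testing at each study visit". Baseline strength is therefore planned for everyone.
- Sample size: alpha 0.05, with SD and target difference of "0.22 Nm/kg and 0.15 Nm/kg, respectively", from which "a sample size of 70 total patients (35 patients per group) would be 80% powered to detect clinically important differences". No baseline correlation enters the calculation.
- Secondary outcomes: "All continuous secondary variables will be assessed using group x time repeated measures ANOVAs". This is the only planned analysis in which a preoperative value could play a part, and it does not cover the primary comparison.

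The supplied text contains no ANCOVA, change-score analysis or other baseline adjustment of the primary outcome.

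**The concern.** Preoperative strength is the same measurement on the same person, so it is a natural candidate to explain part of the between-person spread at 2 weeks. A t-test on the 2-week values leaves that spread in the error term. It also lets any chance preoperative difference between the arms pass into the estimate, in proportion to the correlation. With 35 per arm, adults aged 18 to 85 of both sexes, and no stratified randomization described in the supplied text, some chance difference is to be expected.

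This matters more here because the design has little reserve. The power calculation needs 70 evaluable patients and Study Design plans to enrol 70. The maximum of 73 on the Project Information page is not tied to the power calculation. Any missing 2-week strength test takes the trial towards or below its stated 80%.

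**Working it through.** **Inputs.** From Study Design: SD 0.22 Nm/kg, difference 0.15 Nm/kg, two-sided alpha 0.05, 35 per arm. Assumed, because the documents do not give it: r, the within-arm correlation of preoperative and 2-week strength, shown from 0 to 0.7.

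**1. The plan's own figure.** Standardized difference: 0.15/0.22 = 0.682. Standard error of the difference: 0.22 × √(2/35) = 0.0526. Noncentrality: 0.15/0.0526 = 2.85. The noncentral t distribution with 68 degrees of freedom gives power of 80.3%, and 35 is the smallest number per arm that reaches 80%. The stated sample size is right for the stated test.

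**2. ANCOVA with the same patients.** Residual SD = 0.22 × √(1 − r²), with 2 × 35 − 3 = 67 degrees of freedom. The half-width of the 95% CI is 1.996 × residual SD × √(2/35). For the t-test it is 1.995 × 0.0526 = 0.105.

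| r (assumed) | Residual SD | Power, 35 per arm | n per arm for 80% power | 95% CI half-width (Nm/kg) |
|---|---|---|---|---|
| t-test | 0.220 | 80.3% | 35 | 0.105 |
| 0 | 0.220 | 80.3% | 35 | 0.105 |
| 0.2 | 0.216 | 81.8% | 34 | 0.103 |
| 0.3 | 0.210 | 83.8% | 32 | 0.100 |
| 0.5 | 0.191 | 90.1% | 27 | 0.091 |
| 0.6 | 0.176 | 94.0% | 23 | 0.084 |
| 0.7 | 0.157 | 97.6% | 19 | 0.075 |

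**3. Missing 2-week data.** Same formulas with fewer evaluable patients:

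| Evaluable per arm | t-test | ANCOVA, r = 0.3 | ANCOVA, r = 0.5 |
|---|---|---|---|
| 35 | 80.3% | 83.8% | 90.1% |
| 33 | 77.9% | 81.6% | 88.3% |
| 30 | 73.8% | 77.7% | 85.0% |

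**4. Chance baseline imbalance.** Assume the preoperative SD is also 0.22. The baseline difference between arms then has standard error 0.0526. A one-standard-error imbalance moves the expected unadjusted 2-week difference by r × 0.0526:

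| r (assumed) | Shift (Nm/kg) | Share of 0.15 |
|---|---|---|
| 0.2 | 0.011 | 7% |
| 0.3 | 0.016 | 11% |
| 0.5 | 0.026 | 18% |
| 0.7 | 0.037 | 25% |

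**5. Change scores are not the remedy.** With equal SDs the change-score SD is 0.22 × √(2(1 − r)). At r = 0.3 this is 0.260, and power falls to 66.2%. At r = 0.5 it is 0.220, and power only equals the plan's 80.3%.

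**The case against.** The strongest reply is that nothing is wrong as written. Randomization makes the t-test valid, type I error is 5%, and the sample size matches the test. That stands: this is neither a bias nor a sample-size error. Chance imbalance is already reflected in the t-test's standard error, so the imbalance shift and the lost precision are two views of one cost and should not be added together.

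The size of the gain rests on a correlation that the documents do not supply. That also stands. The correlation could be low: the background text links quadriceps dysfunction to postoperative swelling, which preoperative strength need not predict. At r = 0.2 the gain is only 1.5 percentage points. The recommendation survives because the cost at r = 0 is negligible.

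The plan does not say whether the 0.22 SD, taken from a cited study, describes raw, change or adjusted values. If it is already a baseline-adjusted SD, ANCOVA would have about the stated 80% rather than more, and the raw SD would be larger: at r = 0.5 it would be 0.22/√(1 − 0.25) = 0.254, giving the planned t-test about 68% power. If it is a change-score SD, the raw SD is 0.22/√(2(1 − r)), which exceeds 0.22 only when r is above 0.5. The figures move in each case, but the preference for ANCOVA does not.

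Two smaller points hold. Baseline is left out of the primary test only, since the secondary repeated measures analyses may include the preoperative visit. And baseline testing is planned rather than guaranteed, because the Potential Risks & Benefits section lets a session's functional testing be skipped if judged unsafe.

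**Conclusion.** The concern holds as a point of efficiency and robustness that should be addressed. The primary analysis leaves out a baseline measurement that the trial collects for every participant by design. Under the plan's SD and difference, adjustment would raise power from 80.3% to between 81.8% (r = 0.2) and 97.6% (r = 0.7), and would protect against modest loss of 2-week data if the correlation is moderate. These figures assume that 0.22 is the SD of raw 2-week values, that the relation with baseline is linear, and that r lies in the range shown. That preoperative strength is the best available covariate is a reasonable judgement, not something the documents demonstrate. The direction of the advice does not depend on the size of r.

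**What to change.** Replace the primary t-test sentence with an ANCOVA: 2-week isometric quadriceps strength of the operated leg, regressed on treatment group and preoperative strength of the same leg. Report the adjusted mean difference with its 95% confidence interval at two-sided alpha 0.05. Keep the unadjusted t-test as a sensitivity analysis.

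Three details belong with the change:

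- State the leg and trial summary analysed. The Research Procedures section describes testing of both legs and three recorded trials but names neither.
- Give a rule for participants with a missing preoperative value.
- Record and date the change before unblinding. Study Design says the biostatistician is blinded, so this can be done credibly; a decision to adjust made after seeing an imbalance would be open to challenge.

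The cost is a few sentences of analysis text and one degree of freedom, with no added patients, visits or measurements. The sample size can stay at 70.

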- This modification may or will increase risk to study participants.

Is this modification request due to an Unanticipated Problem/Adverse Event, or Protocol Violation?

- Yes
- No

In your professional opinion, does this modification involve information that might relate to a subject's willingness to continue to take part in the research?

- Yes
- No

If yes, state how the information will be communicated to subjects (i.e., re-consent, send letter, etc.):

For each proposed modification, include a justification.

Example: [name], is being added as co-investigator because she has expertise with the subjects on this protocol. She has completed human subject protections training, and is authorized to obtain consent.

We are removing [name] as he is no longer at UK and adding [name] as he will take over data collection/analysis on the project.

PROJECT INFORMATION**0 unresolved
comment(s)**

Title of Project: (Use the exact title listed in the grant/contract application, if applicable).

If your research investigates any aspect of COVID-19, please include "COVID19" at the beginning of your Project Title and Short Title

Comparison to short-duration tourniquet Total Knee Arthroplasty (TKA) with the Aquamantys® bipolar sealer and the standard of care in the setting of outpatient TKA: A randomized, double-blinded study

Short Title Description

Please use a few key words to easily identify your study - this text will be displayed in the Dashboard listing for your study.

Aquamantys

Anticipated Ending Date of Research Project: 5/31/2024

Maximum number of human subjects (or records/specimens to be reviewed) 73

After approval, will the study be open to enrollment of new subjects or new data/specimen collection? Yes No

PI CONTACT INFORMATION

0 unresolved
comment(s)

Principal Investigator (PI) role for E-IRB access

The PI is the individual holding primary responsibility on the research project with the following permissions on the E-IRB application:

1. Read;
2. write/edit;
3. receive communications; and
4. submit to the IRB (IR, CR, MR, Other Review*).

If research is being submitted to or supported by an extramural funding agency such as NIH, a private foundation or a pharmaceutical/manufacturing company, the PI listed on the grant application or the drug protocol must be listed as PI here.

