Describe and explain the study design (e.g., observational, secondary analysis, single/double blind, parallel, crossover, deception, etc.).

- *Clinical Research:* Indicate whether subjects will be randomized and whether subjects will receive any placebo.
- *Community-Based Participatory Research:* If you are conducting [community-based participatory research \(CBPR\)](#), describe strategies for involvement of community members in the design and implementation of the study, and dissemination of results from the study.
- *Qualitative research:* Indicate ranges where flexibility is needed, if a fixed interview transcript is not available, describe interview topics including the most sensitive potential questions.
- *Research Repositories:* If the purpose of this submission is to establish a Research Repository (bank, registry) and the material you plan to collect is already available from a commercial supplier, clinical lab, or established IRB approved research repository, provide scientific justification for establishing an additional repository collecting duplicate material. Describe the repository design and operating procedures. For relevant information to include, see the [UK Research Biospecimen Bank Guidance](#) or the [UK Research Registry Guidance](#).

This is a single site, randomized, double-blind study which will be conducted at the University of Kentucky. This study intends to enroll 70 male and female participants. Participants will be randomized to have TKA either with the aforementioned short-duration tourniquet TKA protocol with Aquamantys or the standard of care (tourniquet used throughout the case with no Aquamantys). Provided patient meet the functional goals necessary for discharge, all patients will be discharged to home on the day of surgery or on postoperative day 1. Participants will be blinded during the course of the study to their assigned group, as will the study personnel performing postoperative assessments and the study's biostatistician.

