Five Times Sit-to-Stand Test: The five-repetition sit-to-stand is commonly used to measure mobility and function in older adults. Participants are positioned in a standard 16" office chair with their arms at their sides and back located against the back of the chair. Participants are instructed to "Please stand up straight as quickly as you can 5 times, without stopping in between. Keep your arms folded across your chest. I'll be timing you with a stopwatch. Ready, begin." The test is timed using a stopwatch and the timer is stopped when the individual achieves a standing position on the 5th trial. To ensure safety, we will utilize a four-legged chair that does not have wheels, and the chair will be placed so it backs against a wall to prevent the chair from moving during the test. While the participant will be asked to complete the test without using the chair's armrests, the armrests are available for balance should they need assistance. If at any visit the participant cannot complete one practice repetition of sit to stand without using the armrests, we will not ask them to participate in the test at that visit.

Patient-Reported Outcomes: Participants will be asked to complete four questionnaires at each study visit. Participants will be asked to complete the Knee injury and Osteoarthritis Outcome Score, Joint Replacement (KOOS JR) questionnaire which is a 7-item instrument validated to assess patient outcomes following knee arthroplasty. Other questionnaires will include the Veterans Rand-12 (VR-12) which is a 12-item instrument that assesses physical and mental health and a Visual Analogue Scale (VAS) to assess pain and patient confidence in their knee. In addition, a study-specific questionnaire will be used to assess whether the patient is able to ambulate without an assistive device and to determine the method by which the patient navigates stairs (one-step at a time, requires the use of a handrail, etc.).

Attachments

Attach Type	File Name
ResearchProcedures	Aquamantys Page 4 Study Flow Chart.pdf

Data Collection & Research Materials

In this section, please provide the following:

- Describe all sources or methods for obtaining research materials about or from living individuals (such as specimens, records, surveys, interviews, participant observation, etc.), and explain why this information is needed to conduct the study.

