Describe why potential benefits are reasonable in relation to potential risks. If applicable, justify why risks to vulnerable subjects are reasonable to potential benefits.

Aquamantys Bipolar Sealer: Delicate body structures could be damaged by hot saline run-off. We will use proper suctioning and other protective measures during surgery to reduce this risk.

Isometric Quadriceps Strength and Sit-to-Stand Testing: The possible risks for participation in this study are minimal. Participants may injure their leg during the performance of the functional testing; however, all precautions will be taken to prevent this. All functional testing will be carried out by a trained member of the research team. It is also possible that some participants may experience muscle soreness following the strength and functional testing. However, this soreness will not be significantly greater than that which they may experience in response to starting a new exercise during physical therapy. If the functional testing is deemed unsafe for the participant to complete they will not complete the testing at that session.

Participation in the study may not result in any benefits to participants. This study may help doctors better understand different materials used in hip replacements that may help others in the future.

Available Alternative Opportunities/Treatments

Describe alternative treatments or opportunities that might be available to those who choose not to participate in the study, and which offer the subject equal or greater advantages. If applicable, this should include a discussion of the current standard of care treatment(s).

There are no alternative treatments to this study other than not participating in this study. The participant may receive either short or long duration tourniquet use without being in the study as both methods of surgery are currently utilized.

[Back to Top](#)

Records, Privacy, and Confidentiality

Specify where the data and/or specimens will be stored and how the researcher will ensure the privacy and confidentiality of both. Specify who will have access to the data/specimens and why they need access.

Describe how data will be managed after the study is complete:

- If data/specimens will be maintained, specify whether identifiers will be removed from the maintained information/material.
- If identifiers will not be removed, provide justification for retaining them and describe how you will protect confidentiality.

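### Would a 2-week strength test skipped for safety undermine the primary t-test?

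*Combined protocol and SAP*

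**What the plan says.** The primary analysis is set out under Study Design: "The primary outcome variable, isometric quadriceps strength at 2 weeks, will be compared between groups using a two-tailed independent t-test". The same section gives the sample size: "a sample size of 70 total patients (35 patients per group) would be 80% powered to detect clinically important differences", using an SD of 0.22 Nm/kg, a difference of 0.15 Nm/kg and alpha 0.05. Enrolment is described as "This study intends to enroll 70 male and female participants", while the application field under Project Information reads "Maximum number of human subjects (or records/specimens to be reviewed) 73". Nothing explains the 3 extra places.

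Study Design schedules strength testing at all four visits. Sit-to-stand comes later: "Beginning at the 6-week postoperative visit, patients will be asked to complete the five times sit-to-stand test". It also has its own exemption under Research Procedures, which begins "If at any visit the participant cannot complete one practice repetition of sit to stand without using the armrests".

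The text at issue is under Potential Risks & Benefits. The paragraph opens "Isometric Quadriceps Strength and Sit-to-Stand Testing: The possible risks for participation in this study are minimal" and ends "If the functional testing is deemed unsafe for the participant to complete they will not complete the testing at that session".

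The supplied text defines no analysis population and has no rule for a missing 2-week value, no sensitivity analysis and no allowance for dropout. The study flow chart and data-collection forms are attachments that were not supplied.

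**The concern.** At 2 weeks the strength test is the only physical test scheduled, so a skip rule that covers it acts directly on the primary outcome. A t-test uses only participants who have a value, so anyone untested drops out of the comparison.

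The decision to skip comes after randomisation and could depend on how weak the knee is. The protocol's own rationale is that the short-tourniquet procedure may preserve quadriceps function and lower fall risk. If so, participants judged unsafe to test could be commoner in the standard-care arm, and they would be the ones carrying the effect. Recruiting a few more people would restore the number of values but not the comparison of everyone randomised.

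At stake would be a diluted estimate if the weakest are lost from both arms, or a spurious difference if they are lost from one. Either could look like a complete analysis of 70.

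**Working it through.** **1. The plan's own figure.** Inputs from Study Design: SD 0.22, difference 0.15, two-sided alpha 0.05, 35 per group.

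- Standardised difference: 0.15 / 0.22 = 0.682.
- Noncentrality: 0.682 × √(35/2) = 2.85, on 68 degrees of freedom.
- Power from the noncentral t distribution: 80.3%.
- Solving for 80% power gives 34.75, rounded up to 35 per group.

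The stated 70 and 80% reproduce.

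**2. Loss of numbers alone.** With 35 against 32 analysed (3 of 70 lost, no replacement), noncentrality is 0.682 × √(35×32/67) = 2.79 and power is 78.4%. With 73 enrolled and 3 untested, 73 − 3 = 70 and power is again 80.3%. Lost numbers are a minor matter.

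**3. Selective loss.** This needs assumptions the documents do not supply. In the simulations, data are normal with SD 0.22, 37 and 36 are randomised, *k* participants are untested, and the t-test is run on the rest. The value *k* = 3 is only the gap between 73 and 70; it is not a documented loss rate.

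| Who is untested | k = 1 | k = 3 | k = 6 |
|---|---|---|---|
| Weakest overall, true difference 0.15: estimate | 0.141 | 0.129 | 0.116 |
| Same: power | 79% | 74% | 67% |
| Weakest of one arm, no true difference: apparent difference | 0.013 | 0.035 | 0.06 |
| Same: false-positive rate | 6% | 12% | 25–26% |

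If 3 are missing at random, the estimate stays at 0.150 and power at 80%. If the weakest overall are missing and there is no true difference, the false-positive rate is about 5% for *k* = 3 and *k* = 6. A common strength cut-off that removes the weakest 5% to 10% of controls shrinks the estimate to 0.132–0.120 and also leaves the false-positive rate near 5%.

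So a skip rule tied to strength and applied alike in both arms dilutes a true effect: (0.150 − 0.129) / 0.150 = 14% at *k* = 3. It does not create a false one. Inflation requires the weakest of one arm to be skipped while equally weak participants in the other arm are tested.

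**4. Do the documents point to that pattern?**

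- *Reach of the safety sentence.* Its heading names both tests, and sit-to-stand already has its own exemption, which favours a wide reading. However, the sentence refers only to functional testing, and the soreness sentence in the same paragraph names strength testing and functional testing as two things. On that narrow reading it covers only sit-to-stand, which starts at 6 weeks, and never touches the primary outcome. The text does not settle this.
- *Link to weakness.* Research Procedures describes a seated, strapped push against a hand-held dynamometer. A weak participant would ordinarily give a low value there, not a missing one.
- *Difference between arms.* Study Design blinds both the participants and the staff who make the postoperative assessments.
- *Frequency.* None is given. The inclusion criteria require the ability to attend visits and complete study procedures.
- *The figure 73.* It is a ceiling in a form field. No text describes replacing untested participants.

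**5. Would a different analysis help?** The obvious candidate is a supporting rank-sum test that gives untested participants the lowest rank. When the 3 weakest of 73 really are the untested, it keeps about 80% power, against 74% for the t-test. When untested status has nothing to do with strength, it does worse:

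| Untested unrelated to strength | Rank-sum | t-test |
|---|---|---|
| 3 at random, difference 0.15: power | 72% | 80% |
| 6 at random, difference 0.15: power | 64% | 78% |
| All 3 in the better arm, difference 0.15: power | 48% | 80% |
| All 3 in one arm, no difference: false-positive rate | about 8% | 5% |
| All 6 in one arm, no difference: false-positive rate | 18–20% | 5% |

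It replaces one untestable assumption with another.

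**The case for a change.** The best case for a change is that it would be cheap and can only be made in time. The reason a test was not done has to be noted at the visit, because it cannot be reconstructed reliably afterwards. Without it, a reader could not separate a harmless gap from a selective one. Blinding prevents deliberate favouritism, but it does not stop selection through strength itself if the treatment affects strength.

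Part of this stands. The supplied text says nothing about a missing 2-week value, and the wording on skipped tests is open to two readings. Selection through strength could dilute a true difference despite blinding.

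The claim that reasons will go unrecorded cannot be established, since the data-collection forms are not in the supplied text and the protocol says all adverse events are recorded. Selection through strength alone, with no true effect, also leaves the false-positive rate at its nominal level. The dilution it causes works against finding a benefit.

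**Conclusion.** No change to the plan follows. What remains is missing detail that a competent analyst fills in as a matter of course: state how many in each arm had a 2-week value, give the reasons for the rest, and, if there are more than one or two, show how the result moves over a range of assumed values for them. None of this alters the primary t-test, the sample size or the 80% figure.

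On the documents' SD and difference, the plausible adverse case is dilution from 0.150 to about 0.129 Nm/kg and a fall in power of about 6 points (80.3% to 74%). That assumes 3 untested who are exactly the weakest of 73. The 12% and 25–26% false-positive rates are extreme one-arm scenarios that nothing in the documents supports, and the opposite end of the range is no bias. The judgement would be different if untested participants proved numerous or clearly uneven between arms, which routine reporting by arm would reveal.
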